12.1.2 Clinical Assessments

Stage I – Substance use screening questions Proposed 4 – Item Screen:

The screen will consist of one stem question with 4 substance categories.

(Instructions: The following questions are about the past 12 months)

Question - In the past 12 months, how often have you:

- **1.** Used any tobacco (for example, cigarettes, e-cigarettes, cigars, pipes, or smokeless tobacco)?
- 2. [Males] Had 5 or more drinks containing alcohol in one day?

[Females] Had 4 or more drinks containing alcohol in one day?

[Only the version specific to participant's gender will be administered].

- 1 standard drink is about 1 small glass of wine (5 oz), 1 beer (12 oz), or 1 single shot of liquor
- **3.** Used any drugs including marijuana, cocaine or crack, heroin, methamphetamine (crystal meth), hallucinogens, ecstasy/MDMA?
- **4.** Used any prescription medications just for the feeling, more than prescribed,, or that were not prescribed for you?

Prescription medications that may be used in this way include:

- Opiate pain relievers (for example, OxyContin, Vicodin, Percocet, methadone).
- Medications for anxiety or sleeping (for example, Xanax, Ativan, Klonopin).
- Medications for ADHD (for example Adderall or Ritalin).

Response Options (regarding the past 12 months):

- Daily or almost daily
- Weekly
- Monthly
- Less than monthly
- Never

	age II - Brief assessment questions \PS Tool (modified ASSIST-Lite)				
(Ir	(Instructions: The following questions are about the PAST 3 MONTHS ONLY)				
1)	Did you smoke a cigarette containing tobacco?	Yes [1] No [0]	\rightarrow No: Skip to Q2		
	1a Did you usually smoke more than 10 cigarettes each day?	Yes [1] No [0]			
	1b Did you usually smoke within 30 minutes after waking?	Yes [1] No [0]	Tobacco score: [0-3]		
			Cut-off = 2		
2)	Did you have a drink containing alcohol?	Yes [1] No [0]	\rightarrow No: Skip to Q3		
	2a On any occasion, did you have 5 or more drinks containing alcohol in a day (for men)/ 4 or more drinks containing alcohol in a day (for women)? *	Yes [1] No [0]			
	2b Have you tried and failed to control, cut down or stop drinking?	Yes [1] No [0]	Alcohol score: [0-4]		
	2c Has anyone expressed concern about your drinking?	Yes [1] No [0]			
	Standard drink is about 1 small glass of wine (5 oz), or 1 eer (12 oz), or 1 single shot of liquor		Cut-off = 3		
3)	Did you use marijuana (hash, weed)?	Yes [1] No [0]	\rightarrow No: Skip to Q4		
	3a Have you had a strong desire or urge to use marijuana at least once a week or more often?	Yes [1] No [0]			
	3b Has anyone expressed concern about your use of marijuana?	Yes [1] No [0]	Cannabis score: [0-3]		
			Cut-off = 2		
4)	Did you use cocaine, crack, or methamphetamine (crystal meth)?	Yes [1] No [0]	ightarrow No: Skip to Q5		
	4a Did you use cocaine, crack, or methamphetamine (crystal meth) at least once a week or more often?	Yes [1] No [0]			
	4b Has anyone expressed concern about your use of cocaine, crack, or methamphetamine (crystal meth)?	Yes [1] No [0]	Stimulant score: [0-3]		
			Cut-off = 2		
5)	Did you use heroin?	Yes [1] No [0]	\rightarrow No: Skip to Q6		
	5a Have you tried and failed to control, cut down or stop using heroin?	Yes [1] No [0]			
	5b Has anyone expressed concern about your use of heroin?	Yes [1] No [0]	Heroin score: [0-3]		
			Cut-off = 2		

These next questions are about taking prescription medications just for the feeling, more than prescribed, or that were not prescribed for you. Please do NOT report use of 'over the counter' medications.

	age II - Brief assessment questions \PS Tool (modified ASSIST-Lite)				
(Ir	(Instructions: The following questions are about the PAST 3 MONTHS ONLY)				
6)	Did you use a prescription opiate pain reliever (for example, Percocet, Vicodin) not as prescribed or that was not prescribed for you?	Yes [1] No [0]	\rightarrow No: Skip to Q7		
	6a Have you tried and failed to control, cut down or stop using an opiate pain reliever?	Yes [1] No [0]			
	6b Has anyone expressed concern about your use of an opiate pain reliever?	Yes [1] No [0]	Opioid score: [0-3]		
			Cut-off = 2		
7)	Did you use a medication for anxiety or sleep (for example, Xanax, Ativan, or Klonopin) not as prescribed or that was not prescribed for you?	Yes [1] No [0]	\rightarrow No: Skip to Q8		
	7a Have you had a strong desire or urge to use medications for anxiety or sleep at least once a week or more often?	Yes [1] No [0]			
	7b Has anyone expressed concern about your use of medication for anxiety or sleep?	Yes [1] No [0]	Sedative score: [0-3]		
			Cut-off = 2		
8)	Did you use a medication for ADHD (for example, Adderall, Ritalin) not as prescribed or that was not prescribed for you?	Yes [1] No [0]	\rightarrow No: Skip to Q9		
	8a Did you use a medication for ADHD (for example, Adderall or Ritalin) at least once a week or more often?	Yes [1] No [0]			
	8b Has anyone expressed concern about your use of a medication for ADHD (for example, Adderall or Ritalin)?	Yes [1] No [0]	Stimulant score: [0-3]		
			Cut-off = 2		
9)	Did you use any other illegal or recreational drug (for example, ecstasy/molly, GHB, poppers, LSD, mushrooms, special K, bath salts, synthetic marijuana ('spice'), whip-its, etc.)?		Not scored –		
Wł	What did you take?				

Stage III – A brief survey of views on use of the screen and TAPS Tool:

As participants complete the self-administered and interviewer-administered screen and TAPS Tool, the RA will record, for each mode of administration, any interruptions during administration of the screen or tool [in minutes], the number of times the participant requests assistance, and the type of assistance requested (reading, comprehension, use of the iPad, or other recorded in comments box).

After the participants complete the screen and TAPS Tool, they will be asked to complete a brief survey asking about the feasibility (e.g., user-friendliness; need for assistance), acceptability (e.g., comprehension, likelihood of responding accurately, user friendliness), and preference for format (self-administration and interviewer-administration) of the tool in primary care settings.

The following survey items will be rated by participants on a 5-point Likert Scale to capture their view of their experience with the interviewer—administered and self-administered versions of the tool.

How much do you agree with the following statements on a scale of 1-5 where:

1 = strongly disagree			
2 = disagree			
3 = neither agree nor disagree			
4 = agree			
5 = strongly agree			
Q1. These questions were easy to understand.			
Q2. I was comfortable answering these questions.			
Q3. I answered these questions as honestly as I could.			
Q4. I would be willing to answer questions like these at my doctor's office.			
Q5. I think my friends would answer these questions honestly at their doctor's office.			
Q6. The iPad touch screen was easy to use.			
Q7. I would prefer that a person asked me these questions in the doctor's office instead of answering them myself on an iPad.			
Q8. I would prefer answering these questions on an iPad instead of having a person ask me.			
Q9. The voice recording was helpful.			
Q10. I would be comfortable sharing my answers about drug use with my doctor.			

Stage IV - Comparison instruments for validation purposes, all of which are administered by the RA in a face-to-face interview

- 1. Full ASSIST: The ASSIST provides substance-specific information and provides scores for each substance. The instrument has been shown to be a valid measure of substance use involvement, with good feasibility, reliability, and validity (Newcombe et al., 2005; WHO ASSIST Working Group, 2002). The ASSIST probes several non-medical use dimensions during the past 3 months and lifetime for specific substances, including tobacco, alcohol, cannabis, cocaine, amphetamine-type stimulants, sedatives, and opioids. It generates substance specific involvement scores with validated cutoffs corresponding to low-risk, moderate-risk, or high-risk use. Each 'past 3 month' item on the ASSIST is rated on a 5-point interval scale of never, once or twice, monthly, weekly, and daily or almost daily, with different corresponding scores for each value depending on the question. Lifetime questions have response categories of either: 'yes' or 'no'; or 'no', 'yes but not in the last 3 months', and 'yes, within the last 3 months'.
- 2. AUDIT-C: The World Health Organization's Alcohol Use Disorders Identification Test consumption items (AUDIT-C) is a widely used and validated measure of unhealthy alcohol use among medical patients. It is a 3-item questionnaire about consumption of alcohol that can be administered by an interviewer or self-administered (we will use only the interviewer administered version). The AUDIT-C will be used as a comparison measure because it is the most widely used and recommended current screening approach in primary care settings, and it collects information that is distinct from that gathered using the CIDI-SAM. (Reinert and Allen 2002, Bradley, DeBenedetti et al. 2007).
- **3. Timeline Follow-Back:** Timeline Follow-Back will be used to assess the use of alcohol, cannabis, heroin, prescription opioids, prescription stimulants, cocaine or crack, methamphetamines, prescription sedatives/hypnotics, and other drugs (e.g., inhalants, hallucinogens) in the past 30 days. This technique, widely used in drug abuse research, consists of a careful review by the RA with the research participant of their substance use over in this case a 30 day time period preceding the interview (Sobell & Sobell, 1992). The RA will use a calendar and review key events (such as birthdays, holidays) to anchor the dates in the month.
- 4. Modified CIDI-SAM-2: The CIDI-SAM-2 will be used to assess tobacco, alcohol and all drug use diagnoses. The CIDI-SAM-2 is a comprehensive instrument used to assess substance use disorders to ICD-10 and DSM-IV criteria (Forman et al., 2004). Substance abuse disorders covered in the CIDI-SAM-2 are alcohol, tobacco, and nine categories of illicit drugs. Questions mapping to the DSM-IV diagnostic criteria for substance abuse and dependence are asked in a past 12 month time frame. In the current study, the CIDI-SAM-2 will be modified by dropping all the questions that are not used to obtain a DSM-5 substance use disorder diagnosis. In addition, the CIDI-SAM-2 question on craving will be retained so that the DSM-5 criteria for substance use disorder can be obtained. We will use the CIDI-SAM-2 as the "gold standard" for identifying DSM-5 substance use disorders (i.e., patients who should be classified as high risk on a screening instrument).
- 5. Fagerström Test for Nicotine Dependence (FTND): (Fagerström et al., 1990; Heatherington et al., 1991). The FTND consists of three yes/no items scored 0 (no) and 1 (yes) and three multiple-choice items scored from 0 to 3. The items are summed to yield a total score of 0-10. Nicotine dependence is classified in the following manner: 0-2 Very low; 3-4 Low; 5 Moderate; 6-7 High; and, 8-10 Very high. The FTND has shown good reliability (Agrawal et al., 2011; Pomerlou et al., 1994), although more research is needed on the diagnostic validity of the FTND (Meneses-Gaya et al., 2009).

- 6. Smokeless Tobacco Questionnaire: (Institute of Medicine, 2007; American Cancer Society Cancer Action Network, 2012). Smokeless tobacco is a problem that has been associated with oral cancer (Harris et al., 2013). For this reason, data will be collected on the past 3 month use of such tobacco products. Did you use any smokeless tobacco product (snus, dissolvable tobacco tablets, chewing tobacco, or any other product containing tobacco) for more than 5 times a day? Did you use any smokeless tobacco product (snus, dissolvable tobacco tablets, chewing tobacco, or any other product containing tobacco) for more than 10 times a day? Did you usually use a smokeless tobacco product within 30 minutes after waking? Did you use e-cigarettes (yes/no). If yes, how many times per day?
- 7. Oral fluid samples for biological measures of objective validation: All participants will be invited to provide an oral fluid sample to test for amphetamines, methamphetamine (MDMA), cocaine/metabolite, opiates, oxycodone, phencyclidine, THC, barbiturates, benzodiazepines, and methadone. Samples can be analyzed by enzyme immunoassay (EIA). Oral fluid testing has been found to have adequate reliability compared to urine testing. (Bosker & Huestis, 2009; Cone & Huestis, 2007).

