2.5 Assessment

- 1. The TAPS Tool will consist of a 4-item screen for tobacco use, alcohol use, prescription medication misuse, and illicit substance use in the past year and a brief assessment (modified version of the ASSIST-Lite (Ali et al., 2013)).
- 2. Participants will complete a brief survey on their view of the screen and tool's feasibility, acceptability, and their preference for format of administration of the screen and tool (self-administration vs. interviewer-administration).
- 3. Validation assessments include interviewer administered: (a) full ASSIST, (b) 30-day Timeline Follow Back (TLFB) for alcohol, prescription drug misuse, and illicit substance use, (c) modified Composite International Diagnostic Interview – Substance Abuse Module Version 2 (CIDI-SAM V2) for alcohol and all prescription drug and illicit substance use disorder diagnoses, (d) Fagerström Test for Nicotine Dependence (FTND), (e) the smokeless tobacco questionnaire, and, (f) AUDIT-C, (g) oral fluid testing for amphetamines, methamphetamine (including ecstasy/MDMA), cocaine/metabolite, opiates, oxycodone, phencyclidine, THC, barbiturates, benzodiazepines, and methadone.

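### Prescription misuse is worded inconsistently across the Stage I item, the Stage II stems, item 8a and the TLFB description, so prescribed use can supply the point that reaches the ADHD-medication cut-off

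*Protocol*

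**What the plan says.** All item wording is in Protocol Section 12.1.2.

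- **Stage I, item 4** asks about the past 12 months: "Used any prescription medications just for the feeling, more than prescribed,, or that were not prescribed for you".
- **Stage II lead-in**, printed once before Q6, repeats that definition: "These next questions are about taking prescription medications just for the feeling, more than prescribed, or that were not prescribed for you".
- **Stage II stems** change the formula. Q6 reads "Did you use a prescription opiate pain reliever (for example, Percocet, Vicodin) not as prescribed or that was not prescribed for you" and Q8 reads "Did you use a medication for ADHD (for example, Adderall, Ritalin) not as prescribed or that was not prescribed for you". Q7 follows the same pattern. A No on any stem skips its follow-ups.
- **Follow-ups 6a to 8b** name the medication without repeating any misuse qualifier. Item 8a is a frequency question: "Did you use a medication for ADHD (for example, Adderall or Ritalin) at least once a week or more often".
- **Scoring.** Each of the three prescription scores runs from 0 to 3, with a cut-off of 2.
- **TLFB.** Stage IV says "Timeline Follow-Back will be used to assess the use of alcohol, cannabis, heroin, prescription opioids, prescription stimulants", and prescription sedatives appear later in the same list. Section 2.5 describes the instrument differently: "30-day Timeline Follow Back (TLFB) for alcohol, prescription drug misuse, and illicit substance use". Section 8.2 names the TLFB among the criterion measures.

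**The concern.** The tool is meant to detect misuse, and the protocol defines misuse in two places. The scored items do not hold to that definition.

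The stems take in any departure from the prescription. On a literal reading that includes missed or reduced doses, which the definition leaves out. Item 8a then asks how often the drug is taken, not how often it is misused. A patient on a daily ADHD prescription answers Yes to 8a because of the prescription itself. That answer is worth one point out of the two needed.

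On the criterion side, two sections disagree on whether the TLFB counts use or misuse of prescription drugs. If use is what gets recorded, participants who correctly deny misuse on the TAPS Tool would appear as missed cases against that criterion.

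Later analysis cannot repair the item wording. Once answers are collected, a Yes on 8a from therapeutic use cannot be told apart from a Yes arising from misuse.

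**Working it through.** **Step 1. Reproduce the printed score range.** Q8, 8a and 8b each score 1 for Yes and 0 for No, and No on Q8 skips the other two. The possible patterns are:

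| Q8 | 8a | 8b | Score | At or above 2 |
|---|---|---|---|---|
| No | skipped | skipped | 0 | no |
| Yes | No | No | 1 | no |
| Yes | No | Yes | 2 | yes |
| Yes | Yes | No | 2 | yes |
| Yes | Yes | Yes | 3 | yes |

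The range 0 to 3 reproduces. Yes on the stem plus Yes on one follow-up is enough for the cut-off.

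**Step 2. Apply the wording to three patients who take a prescribed ADHD drug at least weekly, with 8b = No.**

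| Patient | As printed, read literally | If stem and 8a follow the lead-in definition |
|---|---|---|
| Takes it only as prescribed | Q8 No, score 0 | score 0 |
| One extra dose in 3 months | 1 + 1 = 2 | 1 + 0 = 1 |
| Skipped doses, nothing else | 1 + 1 = 2 | score 0 |

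The second patient has taken more than prescribed and so meets the Stage I definition. The stem point is right; the 8a point comes from therapeutic use. The third patient depends on the literal stem.

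**Step 3. Check the other follow-ups.** 6a asks about failed attempts to control use, 7a about a weekly urge, and 6b, 7b and 8b about concern from others. Taking a drug as prescribed does not in itself produce a Yes on any of these. Only 8a has the fault.

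**Step 4. Scale on the index side (assumed rates).** Take N = 2,000 and criterion prevalence 5%, so 1,900 non-cases. If 0.5% to 5% of participants are under-users who also endorse a follow-up, there are 10 to 100 added false positives. The loss of specificity is 10/1,900 = 0.5 points to 100/1,900 = 5.3 points. For a rarer condition, assume 20 cases, 4 false positives from other causes, and 20 added by wording. Specificity then goes from 1,976/1,980 = 99.8% to 1,956/1,980 = 98.8%, about one point.

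**Step 5. Scale on the TLFB side (assumed rates).** Suppose the TLFB counted any use, 5% misuse a class, a further 5% to 20% only use it as prescribed, and the tool detects misuse perfectly. Apparent sensitivity is misuse / (misuse + prescribed-only use):

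- 5% prescribed only: 5/(5 + 5) = 50%
- 10%: 5/(5 + 10) = 33%
- 20%: 5/(5 + 20) = 20%

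These figures apply only if Section 2.5 is disregarded.

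**The case against.** Several stronger readings are tempting, and the protocol does not support them.

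- **That legitimately prescribed patients in general become false positives.** They do not. No on the stem gives a score of 0. Exposure is limited to those who answer Yes to the stem and then to a follow-up.
- **That all three prescription classes have the scoring fault.** Only 8a can be answered Yes through ordinary treatment. Section 13.2 does not list prescription stimulants among the substances for which adequate precision is expected, so 8a bears on a score that was not going to be estimated tightly. The loose stem wording does reach prescription opioids and sedatives, which are on that list.
- **That the lead-in has no force.** It states the intended definition immediately before Q6, and a respondent who carries it forward would answer No for skipped doses. It does not rescue the extra-dose case unless it is also carried down to 8a, whose text does not invite that.
- **That the TLFB criterion is use-based.** The protocol says both things. This is an unresolved conflict, not a settled rule. Other criteria already address the matter: the full ASSIST is described as probing non-medical use, and current prescriptions are logged to interpret the oral fluid test (Section 12.1.1). Nothing says that this log is applied to the TLFB.
- **That the accuracy estimates would be biased on the index side.** The study estimates how the items perform as worded, so a lower specificity caused by wording would be a correct estimate for those items. The objection stands as far as it goes, but an avoidable fault would then be built into the tool being validated.

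The pilot (Section 9.0) foresees refining wording, which may catch the problem. Nothing directs it to this point.

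**Conclusion.** The point holds as one of inconsistent wording with two concrete consequences. First, item 8a lets therapeutic use supply the point that reaches the cut-off for the ADHD-medication score once the stem is Yes: 2 instead of 1 after a single extra dose, and 2 instead of 0 after skipped doses if the stem is taken literally. Second, Sections 2.5 and 12.1.2 conflict on whether a criterion measure counts use or misuse of prescription drugs.

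The size of either effect is unknown. The protocol reports no rate of under-use or prescribed use, so the ranges above show direction and scale only. A reader might infer large damage to predictive value or sensitivity, but that would follow from the rates chosen and not from the document. The correction should be made before main-study data are collected, because it is cheap then and impossible afterwards.

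**What to change.** 1. Put the definition used in Stage I item 4 and the Stage II lead-in into stems Q6, Q7 and Q8, replacing the looser phrase.
2. Restrict 8a to use 'in this way', an expression that Stage I item 4 already employs. Add the same words to 6a, 6b, 7a, 7b and 8b for consistency, although those items are not answered Yes by therapeutic use alone.
3. Reconcile the TLFB description in Section 12.1.2 with Section 2.5 by stating that, for prescription opioids, stimulants and sedatives, only days of misuse by that same definition are counted.

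The cost is a revision of the iPad item text and one sentence in the TLFB description. The items become slightly longer, so comprehension of the revised wording should be checked in the planned pilot.

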2.0 STUDY SYNOPSIS AND SCHEMA

2.1 Study Objectives

This study seeks to develop and validate a 4-item screen and a two-stage screening and brief assessment tool to screen and assess primary care patients for tobacco, alcohol, prescription drug, and illicit substance use and problems related to their use. The screen and two-stage screening and brief assessment tool (the latter hereafter called the Tobacco, Alcohol, Prescription medications, and other Substance [TAPS] tool) will be evaluated via self-administration and via interviewer-administration.

- Aim 1: To develop a screen and a two-stage brief assessment tool (the TAPS Tool) to detect substance use, sub-threshold substance use disorder (i.e., at-risk, harmful, or hazardous use), and substance use disorders of tobacco, alcohol, prescription medications, and illicit substances among primary care patients.
- Aim 2: To examine the validity of both the 4-item screen and the TAPS Tool by comparing them to reference standard screening and assessment measures for substance use, sub-threshold substance use disorder, and substance use disorders.
- **Aim 3:** To determine the feasibility and acceptability of the self-administration and intervieweradministration of the screen and TAPS Tool among adult primary care patients.

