2.2 Study Design

Study procedures will begin with a pilot testing phase in which 30 adult primary care patients across the three study sites will provide feedback on their comprehension of the items, and the feasibility, acceptability, and preference for format of the 4-item screen and the TAPS Tool delivered using an iPad during self-administration and interviewer-administration. Following the pilot phase, 2,000 adult primary care participants will be randomly assigned in counter-balanced order to have the interviewer-administration of the screen and TAPS Tool first or the self-administration of the screen and TAPS Tool first (each participant will have the screen and tool administered both ways). Following administration of the screen and TAPS Tool, participants will be surveyed on their views of feasibility, acceptability and preference for format of self-administration versus interviewer-administration of the screen and TAPS Tool. After the survey is completed, the interviewer will administer criterion measures of use, sub-threshold substance use disorder, and substance use disorder.

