5.2 Secondary Objectives

The secondary objectives are to determine the feasibility (time required to complete the screen and TAPS Tool, need for assistance) and acceptability (liking of the tool) for the self-administered and interviewer-administered versions of the screen and the TAPS Tool, among primary care patients.

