6.0 STUDY DESIGN

6.1 Overview of Study Design

STUDY GROUP:

Eligible participants will be randomly assigned into one of the two groups: GROUP A and GROUP B. Both groups will first complete a demographic questionnaire (age, gender, race, ethnicity, years of education, current employment status, marital status).

GROUP A:

Will first complete a self-administered TAPS Tool on an iPad and then the same tool via a faceto-face interview (also administered on an iPad). Following tool administration, the RA will survey the participant regarding feasibility and acceptability of the interviewer-administered and self-administered versions of the tool. This will include the RA's observations regarding the amount of time it took to complete each format as well as the participant's need for assistance during the tool administration.

GROUP B:

Will first complete face-to-face interviewer-administration and then self-administration of the tool. Following tool administration, the RA will administer the survey and record observations as described above for Group A.

The RA will administer to both Groups the following reference standard assessments for substance use, sub-threshold SUD, and SUD:

- Full ASSIST for all substances.
- AUDIT-C.
- Timeline Follow Back (TLFB) interview.
- Modified CIDI-SAM 2 for all substance use diagnoses (tobacco, alcohol, and drugs).
- Fagerström Test for Nicotine Dependence (FTND).
- Smokeless tobacco questionnaire.
- Oral fluid testing for amphetamines, methamphetamine (including ecstasy/MDMA), cocaine/metabolite, opiates, oxycodone, phencyclidine, THC, barbiturates, benzodiazepines, and methadone. Oral fluid testing will be accompanied by a review of current medications to determine whether any of the drugs included in the oral fluid test are being prescribed. RAs will have medication picture cards from the National Survey on Drug Use and Health as a reference in case a participant is unable to recall the name of a medication.

Blinding:

Participants will not be blinded to study group. The interviewer will be blinded to the sequence of self-administration vs. interviewer-administration until after the patient provides informed consent.

Study Components:

Study components will include:

- An individualized pilot test of 30 adult primary care patients (across the study sites) to obtain feedback on the user-friendliness of the initial versions of the tool.

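### The acceptability survey cannot give separate self-rated acceptability for the self-administered and interviewer-administered versions, although the protocol says both will be captured

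*Protocol*

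**What the plan says.** Aim 3 in section 2.1 reads "To determine the feasibility and acceptability of the self-administration and intervieweradministration of the screen and TAPS Tool". Section 5.2 repeats it as the secondary objective and covers "acceptability (liking of the tool) for the self-administered and interviewer-administered versions of the screen and the TAPS Tool". Section 2.2 adds that participants give views on "feasibility, acceptability and preference for format of self-administration versus interviewer-administration".

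On how this is collected, section 6.1 states for Group A: "Following tool administration, the RA will survey the participant regarding feasibility and acceptability of the interviewer-administered and self-administered versions of the tool". Group B is handled the same way. The assessment table in section 12 lists one survey form, completed by the research assistant (RA). Section 12.1.2, Stage III, then prints one set of ten statements, introduced with "The following survey items will be rated by participants on a 5-point Likert Scale to capture their view of their experience" with the two versions.

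Feasibility is recorded separately. Stage III has the RA note, for each mode, "any interruptions during administration of the screen or tool [in minutes], the number of times the participant requests assistance, and the type of assistance requested". Section 6.1 has the RA observe completion time and need for help for each format.

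**The concern.** The objective is worded per version, but the survey is largely worded per tool. A participant who was comfortable on the iPad and uneasy with the interviewer, or the reverse, has only one place to record comfort, and the answer cannot be assigned to either experience.

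At stake is whether the trial can say how understandable, comfortable and honestly answered each version was in patients' own judgement. Section 4.1.1 lists validity under either mode as an essential feature, so a clinic choosing between modes would want this. Each participant is seen once with no follow-up (section 6.2), so ratings not taken at that visit cannot be recovered.

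**Working it through.** The plan states no figure for this point. The check is a classification of the items, followed by a test of whether the design can recover what the items leave out.

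**Step 1. Classify the ten Stage III items by the mode they refer to.**

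| Items | Content | Mode referred to | Count |
|---|---|---|---|
| Q1-Q5, Q10 | understanding, comfort, own honesty, willingness at the doctor's office, friends' honesty, sharing answers with the doctor | none | 6 |
| Q6, Q9 | touch screen, voice recording | iPad only, no interviewer counterpart | 2 |
| Q7, Q8 | preference for a person over the iPad, and the reverse | both, but relative only | 2 |

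The counts sum to 6 + 2 + 2 = 10. Items that give a rating of each version: 0 of 10. Reading Q9 as a feature of self-administration is an inference from its wording.

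**Step 2. Compare with the stated components of acceptability.** Section 5.2 glosses acceptability as liking, and no item asks about liking of either version directly. Stage III gives comprehension and likelihood of accurate responding as examples. Q1 and Q3 address these, but each gives one answer covering both modes.

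**Step 3. Can the randomised order separate the modes?** Let *s* and *i* be the ratings a participant would give to self-administration and interviewer-administration. A single answer after both can be written as

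y = w·s + (1 − w)·i,

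where the weight *w* is unknown. Taking *w* as constant within each group, the expected difference between Group A (self first) and Group B (interviewer first) is

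(w_A − w_B)·(mean of s − mean of i), plus any order or carry-over effect.

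If both groups weigh the two experiences alike, w_A = w_B and the first term is zero whatever the true mode difference. If they do not, the weights are still unobserved. The contrast therefore describes order and does not estimate mode.

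**Step 4. What remains available by mode.**

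- Time and need for assistance, by format (section 6.1).
- Interruptions, number of requests for help and type of help, by mode (Stage III). Comprehension is one of the types of help.
- Format preference, from Q7 and Q8.
- Agreement of the substance-use answers themselves, since everyone answers in both modes.

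**Step 5. Precision if Q1-Q3 were asked for each mode.** With n = 2,000 completers (section 7.3), SE of the mean paired difference = SD / √n. The protocol gives no standard deviation of the difference, so it is assumed:

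- SD 0.7: 0.7 / 44.72 = 0.016
- SD 1.0: 1.0 / 44.72 = 0.022
- SD 1.5: 1.5 / 44.72 = 0.034

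All are in points on the five-point scale. These figures describe what the change would deliver; they do not measure the size of the present gap.

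**The case against.** The strongest reply is that most of Aim 3 is already served. Feasibility is recorded within participant for each mode, preference is asked directly in both directions, and Aim 3 asks to determine feasibility and acceptability without stating a formal comparison. Section 13.1.1 says the study tests no hypothesis. Help with comprehension is logged by mode, and disclosure by mode can be seen in the substance-use answers, arguably better than through a self-report of honesty. All of this stands, and it rules out three stronger readings that a reader might infer:

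- *That Aim 3's comparison of the versions cannot be made.* The documents do not support this: feasibility and preference can be compared.
- *That completion time is not collected.* Stage III does not repeat it, but section 6.1 requires it for each format.
- *That the preference result will favour the interviewer.* The protocol gives no evidence of size or direction. Sections 6.1 and 12 assign the survey to the RA, while Stage III speaks of participants completing and rating it, so how answers are entered is not clearly fixed. Bias from answering to the person who conducted the interview is a risk, not a shown result.

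The reply does not reach the six items without a mode. Logged requests for help and agreement of answers are not self-ratings of understanding, comfort or honesty, and a preference between two versions does not show whether either is acceptable.

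**Conclusion.** The point holds for self-rated acceptability. As printed, the survey yields pooled ratings on six of its ten items, one-sided ratings on two and relative preferences on two. Separate ratings of the two versions are therefore unavailable, although sections 5.2 and 12.1.2 say that acceptability of, and experience with, both will be captured. No analysis of the resulting data can supply them.

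This assumes that the list is asked once. That is inferred from the single survey step in section 6.1 and the single form in section 12; nothing says the items are repeated for each mode. The consequence is limited to part of a secondary objective and leaves the validity aims untouched. It merits correction because the data cannot be gathered later and the change is small.

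**What to change.** In section 12.1.2, Stage III, ask at least Q1-Q3 once for each mode in paired wording, for example *when you answered on the iPad* and *when the interviewer asked you*. Report the within-participant difference for each item.

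Preferably have these items and Q7-Q8 self-completed on the iPad, so that the participant is not answering to the RA who conducted the interview, and state this consistently in sections 6.1, 12 and 12.1.2.

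The cost is about three extra Likert items, estimated at under a minute in a visit planned at 30 minutes to 1 hour, plus the matching change to the survey form. If the survey is left as it is, section 5.2 and the Stage III introduction should say that Q1-Q5 and Q10 describe the tool across both modes combined.
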